**Medical University of South Carolina
Protocol**

PI Name: [name].

Study Title: Effect of Cognitive Behavioral Therapy and Transcranial Direct Current Stimulation (tDCS) on Fibromyalgia Patients.

TABLE OF CONTENTS

1. Specific Aims.....	1
2. Background and Significance.....	1
3. Preliminary Studies.....	3
4. Research Design and Methods.....	6
5. Protections of Human Subjects.....	9
6. References/Literature Citations.....	12
7. Facilities Available.....	16

A. SPECIFIC AIMS

Aim: Determine the effects of CBT, anodal tDCS over left DLPFC, and combined CBT+tDCS on clinical pain and functioning among a sample of patients with fibromyalgia

Hypothesis 1a: CBT alone will be associated with significant improvements in pain and functioning

Hypothesis 1b: Anodal tDCS plus CBT will yield significant improvements in pain and functioning that exceed those of CBT alone.

This study will be the first randomized, double-blind, controlled study of tDCS technology as an adjunctive pain management strategy for fibromyalgia pain. Data from this trial will likely yield information regarding the feasibility and efficacy of tDCS+CBT as a chronic pain-management approach.

B. BACKGROUND AND SIGNIFICANCE

FIBROMYALGIA (FM): Fibromyalgia is considered to be a multifactorial disorder resulting from the interaction of both genetic and environmental factors, which contribute to its occurrence and expression³. Symptoms of Fibromyalgia include widespread muscle pain, fatigue, disruption in sleep patterns, loss of memory, and mood disorders. Fibromyalgia is commonly associated with other medical conditions such as depression, rheumatoid arthritis, and other stress-related disorders such as posttraumatic stress disorder. The cause of fibromyalgia is unknown; the most prevalent theory being that those suffering from the disease have a lower threshold for pain due to an increased reactivity of pain sensitive nerve cells. The pain and physical debility of this disease produce changes in nearly every area of life. The prevailing medical treatments are aimed at suppression of symptoms, analgesia, and prevention of damage to joints, but these treatments can have adverse side-effects. Therefore, several non-pharmacological pain management techniques have emerged²⁻⁸.

PAIN AND THE BRAIN: Pain is a complex experience that has sensory-discriminatory, motivational-affective and cognitive-evaluative dimensions⁶. Experimental and clinical fMRI findings suggest that parietal areas, including the primary somatosensory cortex, are mainly involved in the sensory-discriminative dimension of pain experience and frontolimbic networks and the anterior cingulate cortex (ACC) are involved in the affective dimension^{7 8, 9 7, 10 11-13 14, 15 16}. The role of the left prefrontal cortex in

(PFC) pain control is unclear however, there is evidence to support the concept that left PFC activation is negatively correlated with pain unpleasantness¹⁷ suggesting a possible governing role of the PFC on the affective dimension of pain experience¹⁸. Recent studies of expectancy and cognitively-mediated analgesia seem to suggest that cognitive effects on pain perception may involve genuine analgesia mediated by μ -opioid systems^{19, 20} that is associated with decreased activation of the thalamus, insula and ACC. These effects correlate with prefrontal cortex activation²¹. Thus, prefrontal activation/stimulation might result in analgesic effects, presumably by modulating limbic response to pain.^{22 23 24}

MINIMALLY INVASIVE BRAIN STIMULATION AND PAIN: There is some evidence that electrical stimulation of the motor cortex can ameliorate pain²⁵⁻²⁸. The PFC is another studied target for pain relief, and may be specifically helpful in reducing the affective dimension of pain. Stimulation of the PFC increases thermal pain thresholds in healthy adults²⁴ and reduces neuropathic²⁹ and fibromyalgia pain^{23 30}. tDCS involves the application of low-amplitude electric current to the brain. A battery-powered current generator is attached to two sponge electrodes soaked in saline and held in place by a non-conducting montage. Sufficient current penetrates the brain and modifies transmembrane neuronal potential^{31, 32 33} influencing excitability and modulating the firing rate of neurons. Anodal tDCS applied over the human cortex increases excitability, while cathodal tDCS applied over the same area decreases it^{34 35 36, 37 38}. While tDCS appears to have direct effects on brain activity, structure, and neuronal organization, the effects are likely mediated by several factors, the most important of which may be the activity of the brain during stimulation. It appears that tDCS may be a brain stimulation tool that can be used to facilitate or inhibit endogenous cortical and subcortical processes, but not necessarily directly or independently engender large, directly observable behavioral changes unless strategically combined with specific brain activity patterns. This notion has already been embraced in the area of stroke rehabilitation wherein tDCS is combined with rehab therapy to produce significantly enhanced recovery effects.³⁹

COGNITIVE AND BEHAVIORAL ASPECTS OF PAIN PERCEPTION:

Cognitive Behavioral Therapy (CBT) for Pain: CBT is emerging as an important adjunct to medical treatment for FM. CBT for FM is typically aimed at improving pain coping skills and targeting behaviors associated with exacerbation of fatigue and physical disability. The conceptualization of pain as having both cognitive and emotional components paved the way to the assumption that changing a patient's thoughts and attitudes may alter his/her subjective experience of pain. To date several promising controlled investigations of cognitive behavioral therapy (CBT) for FM have been conducted^{1-3 4}. The CBT packages that were applied in these studies generally consisted of the following standard procedures: relaxation training, cognitive pain coping strategies, and self-management strategies. Overall, these studies provide good evidence for the effectiveness of brief CBT in FM compared to an attention placebo, patient education, symptom monitoring and/or no treatment control conditions. CBT for chronic pain is associated with increased activation in the ventrolateral prefrontal/lateral orbitofrontal cortex⁴⁰ and may activate a cortical control mechanism over pain experience. Given the ability of tDCS to enhance cortical excitability in targeted brain areas, it is possible that combining CBT with prefrontal tDCS could enhance the overall effect and possibly its duration.

Pain Catastrophizing or cognitive characterizations of pain as awful, horrible and unbearable, is increasingly being recognized as an important factor in the experience of pain.^{41 42-46} Catastrophizing appears to augment pain by enhancing attention to painful stimuli, and heightening emotional responses.⁴⁷ Catastrophizing is associated with increased activity in the ipsilateral claustrum, cerebellum, DLPFC, parietal cortex, dorsal ACC, medial frontal cortex, and lentiform nuclei⁴⁷ suggesting that pain catastrophizing is significantly associated with increased activity in brain areas related to anticipation of pain, attention to pain, and emotional aspects of pain.

Pain and Cognitive-Behavioral Distraction: Emotional and attentional states appear to contribute to the multidimensional pain experience⁴⁸, and pain can be therapeutically reduced by cognitive manipulation and distraction tasks.⁴⁹⁻⁵² The DLPFC appears to exert active control on pain by modulating cortico-subcortical and cortico-cortical pathways¹⁷ and distraction significantly increases activation of the

cingulo-frontal cortex including the orbitofrontal and perigenual ACC, as well as the PAG and the posterior thalamus.⁵³ These findings suggest that the cingulo-frontal cortex may exert top-down influences to gate pain during distraction.

Pain and Autonomic Regulation: Relaxation-training aimed at decreasing physiological arousal is a standard component of CBT for pain.⁵⁴ Several neuroimaging studies suggest that during relaxation, brain areas including ACC and insula provide a link between cognitive behavior and autonomic bodily responses.⁵⁵⁻⁵⁸ Activity in these areas can have modulatory effects on autoregulatory processes⁵⁸⁻⁶⁰

Pain and Perceived Control: There is now convincing evidence that acute and chronic pain are perceived as less intense when they are or appear to be controllable^{61 62 63 64}. Further, perceived control has been shown to attenuate cortical and subcortical responses to pain.^{65 66-68} Perceived control over pain is associated with activation in dorsal ACC, right dorsolateral, and bilateral anterolateral PFC and activation in ACC and PFC is negatively correlated with pain intensity ratings.^{61, 65} It may be that prefrontal activation via CBT and/or tDCS in chronic pain patients could provide a reinforced cortical governance signal to limbic regions.⁶⁹ This might result in reduced pain behaviors, symptoms, longer-term benefit & improved coping.

C. PRELIMINARY STUDIES

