
Carretero et al⁹⁶ recently attempted to replicate the Sampson findings using similar parameters but in a larger sample with randomization and a single-blind sham controlled arm. 14 subjects underwent real TMS and 12 received sham. The real rTMS was employed with DANTEC TMS equipment at the R-DLPFC location. Subjects received 1 Hz TMS for 60 seconds on and 45 seconds off at 110% MT for approximately 30 minutes for a total of 1200 pulses per session. Subjects received 20 daily sessions in total. Both groups improved in fatigue and CGI but there was no improvement in pain and depression. Furthermore there was no significant difference between real and sham TMS in this sample. However, the sham system was suboptimal with simply a shift in the TMS coil to 45 degrees so that sound is heard but no cutaneous sensation was experienced. More importantly subjects received 400 fewer pulses per session for a total of 8000 fewer pulses than the Sampson group. Thus subjects may have been relatively “underdosed” in comparison, but they failed to replicate the TMS FM treatment effect with right-sided, prefrontal, slow-TMS treatment.

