COMBINED CBT and tDCS INTERVENTION EFFECTS ON PAIN PERCEPTION: To directly address the aims of the present proposal, in a recent preliminary pilot, the Investigators examined the effects of anodal versus cathodal tDCS over the left DLPFC in combination with a laboratory CBT intervention on thermal pain tolerance in 8 healthy volunteers. Participants underwent repeated heat tolerance testing using the Medoc Pathway system before, during and after the combined tDCS+CBT intervention. Participants were randomly assigned to receive anodal or cathodal tDCS delivered over the left DLPFC. For this preliminary pilot, participants all listened to a recording of a laboratory-version of a CBT intervention that focused on 3 distinct elements: 1) identification of catastrophizing language and replacement with more realistic and attenuated linguistic tags for thermal experiences. 2) identification and challenging of automatic negative self-effacing thoughts related to the tolerance task, and 3) a behavioral distraction strategy. Anodal tDCS applied to the left DLPFC during the CBT intervention was associated with a significant increase in thermal pain tolerance whereas cathodal stimulation appears to have blunted the analgesic benefit of the CBT intervention. Despite all subjects receiving the same CBT intervention, those that received simultaneous anodal stimulation of the left DLPFC found the CBT intervention significantly more helpful ($p<.05$) and found the strategies presented more useful in improving pain tolerance ($p<.05$) than those who received cathodal stimulation. These findings support the notion that engaging cognitive neural circuits that have been shown to play a role in the

down-regulation of pain experience and then exciting the circuits with tDCS might offer synergistic benefit.

D. RESEARCH DESIGN AND METHODS (including data analysis)

OVERVIEW: Pilot clinical trial-- Patients with FM will receive a brief course (6 sessions) of manualized CBT for pain (or education-only control) combined with anodal or sham tDCS over the left DLPFC

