THE BECK DEPRESSION INVENTORY (BDI) is a well-researched, brief self-report depression-screening instrument. This instrument will be used for screening purposes in the laboratory study and to characterize depression in the clinical cohort. The BDI scale assesses suicidal ideation, those patients exhibiting suicidal ideations will be referenced to a therapist in order to further manage their depressive symptoms.

THE BECK ANXIETY INVENTORY (BAI) is a well-researched, brief self-report anxiety-screening instrument. It assesses different aspects of anxiety experience (e.g., physiological, cognitive, behavioral).

THE BRIEF PAIN INVENTORY (BPI) is a self-report questionnaire designed to assess pain intensity and the impact of pain on general functioning, relationships and mood.

DAILY PAIN/MOOD DIARIES will be administered via paper and pencil to patients in the clinical pilot Diaries will assess daily (via VAS) average pain, pain at its worst, pain unpleasantness, mood, activity level, and will capture hours of sleep and sleep quality ratings.

THE MCGILL PAIN QUESTIONNAIRE (MPQ) is a self-report scale designed to capture the quality and intensity of pain experience. The ratings load onto 4 factors: 1) Sensory, 2) Affective, 3) Evaluative, and 4) Miscellaneous.

THE MOS SHORT-FORM12 HEALTH SURVERY (SF12) will be used to assess quality of life across the eight QOL domains captured with the measure during the trial.

THE FIBROMYALGIA IMPACT QUESTIONNAIRE will be used to assess pain symptoms and functioning specific to FM.

PROCEDURES:

Clinical Pilot Trial: Patients will be recruited by fliers or referred by providers in the Chronic Pain Clinic, Dept. of Rheumatology and the Behavioral Medicine Clinic at MUSC. Participants will be screened on the telephone, consented, oriented to the study, and instructed in the use of pain diaries. After a 2-week baseline phase, patients will undergo QST. They will then start the manualized CBT intervention in the Behavioral Medicine Clinic at MUSC with simultaneous tDCS (real or sham; randomized and masked). Participants will undergo 1 session per week for 6 weeks. After the last session, participants will undergo another QST session. Patients will continue to complete the pain diaries throughout the treatment as well as a 4-week follow-up phase. At 3 and 6 months, participants will return to the lab to re-complete the dependent measure battery.

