DATA ANALYSIS PLAN AND POWER: Hierarchical Linear Modeling (HLM) will be used to examine changes in pain, sleep and activity over time while controlling for mood (time-series), and controlling for

baseline depression, anxiety and pain scores as a function of group (active vs sham tDCS). HLM will also be used to examine changes in quality of life and functional impairment due to pain. Previous research on the effects of CBT for pain and of tDCS for pain suggests that each is associated with a medium effect-size. To be conservative, assuming that there is no synergistic interaction-effect of combined tDCS and CBT, power is good to detect a group-level main effect ($1-\beta>.80$) with as few as 18 subjects per group. If the interaction-effect is large, as is expected, power is excellent to detect main and interaction effects ($1-\beta>.90$).

E. PROTECTION OF HUMAN SUBJECTS

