1. RISKS TO THE SUBJECTS

The sample will be 72 patients with chronic pain due to FM (BPI pain on average score $>4/10$) between the ages of 21 and 85, with a duration of illness of at least 1 yr and the diagnosis of FM. Interested participants will review and sign the informed consent document with one of the study investigators. Participants will be excluded if they have uncontrolled epilepsy, metal implants in the head or known brain tumors or lesions that intersect the area of stimulation, and severe latex allergies. If a participant indicates the possibility of pregnancy, a urine pregnancy test will be administered. Participants will be excluded from the study if they screen positive for pregnancy. Participants will also be screened for a history of closed head injury with loss of consciousness lasting more than 5 minutes, a history of seizures, a family history of seizures, metal implants above the waist, eczema or other sensitive skin conditions, and current medication usage. These screening measures will be used to assess the risk to benefit ratio for inclusion in the study on a case-by-case basis. If participants indicate on the BDI intent to harm themselves, they will be evaluated by a study psychologist. Pending results of the evaluation, participants will be admitted or hospitalized for appropriate care as necessary. There is no safety data to suggest increased risk for the older population, age 75-85, in this study. There is a possibility of increased skin irritation in this older population.

Targeted/Planned Enrollment Table

Total Planned Enrollment 72

TARGETED/PLANNED ENROLLMENT: Number of Subjects			
Ethnic Category	Sex/Gender		
	Females	Males	Total
Hispanic or Latino	2	1	3
Not Hispanic or Latino	42	27	69
Ethnic Category: Total of All Subjects*	72		
Racial Categories			
American Indian/Alaska Native	1	1	2
Asian	2	1	3
Native Hawaiian or Other Pacific Islander	1	1	2
Black or African American	19	9	28
White	22	15	37
Racial Categories: Total of All Subjects*	45	27	72

b. Sources of Materials

We will collect patient-reported depression, anxiety, sleep, activity, pain scores, and QST scores. All of the data will only contain a unique study identifier. The digital file containing identifying information will be kept on the PI's locked and secure computer. Only the PI and primary research assistant will have access to the identifying information.

c. Potential Risks

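### Hypothesis 1a names no comparator and the stated model has no CBT term, so non-specific improvement could confirm it even if CBT has no effect

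*Combined protocol and SAP*

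**What the plan says.** - **Specific Aims.** The Aim is to determine the effects of CBT, of tDCS and of the two combined. The first hypothesis reads "Hypothesis 1a: CBT alone will be associated with significant improvements in pain and functioning". The second is comparative: "Anodal tDCS plus CBT will yield significant improvements in pain and functioning that exceed those of CBT alone".
- **Section D, Overview.** Patients receive six sessions of "manualized CBT for pain (or education-only control) combined with anodal or sham tDCS over the left DLPFC". This names a control for CBT and implies four cells.
- **Section D, Procedures, and section E.3.** Procedures start patients on CBT after a two-week diary baseline and describe only tDCS as randomised. Section E.3 says all participants might benefit from CBT. Both read as if everyone receives it.
- **Section D, Data Analysis Plan and Power.** The hierarchical linear model examines change over time, adjusted for baseline depression, anxiety and pain, "as a function of group (active vs sham tDCS"). No CBT-versus-education term is named. The power text, however, speaks of main and interaction effects and of 18 subjects per group.
- **Section E.1.** "The sample will be 72 patients with chronic pain due to FM", with a BPI average pain score above 4/10. The BPI is also a dependent measure.

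**The concern.** An aim about the effect of CBT needs a comparison that isolates CBT. Without one, a fall in pain among patients given CBT plus sham tDCS mixes any CBT effect with weekly therapist contact, the passage of time and continuing clinic care. Selecting patients on a pain score can add regression to the mean.

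If 1a is judged on change from baseline, the trial could report that CBT improved pain and functioning without having tested it. The protocol's own Background supports CBT by citing comparisons with attention placebo, education, monitoring or no treatment. Hypothesis 1a as worded falls below that standard, although the overview lists a suitable control.

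**Working it through.** **1. What the text allows.** Hypothesis 1b has a comparator and 1a has none. The stated model separates patients by tDCS only.
- If everyone receives CBT, the time effect in the sham group is an uncontrolled pre-post change under CBT.
- If education-only arms exist but have no model term, that time effect pools CBT and education patients.

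In neither case does the stated model contain a controlled test of CBT.

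**2. Plan figures.** No power or error figure is given for 1a, so there is none to reproduce. The stated power above 0.80 with 18 per group does not bear on this point.

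**3. Inputs.** From the documents:
- total of 72 patients and 18 per group (72/4 = 18 in CBT plus sham with four cells; 72/2 = 36 if everyone receives CBT);
- entry at BPI above 4.

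Assumed, because the documents do not give them:
- BPI SD 2;
- mean before selection 4.5 to 6.0;
- correlation between measurements (rho) 0.6 to 0.8;
- independent measurement errors;
- non-specific improvement (delta) of 0, 0.5 or 1.0 point;
- a paired t-test at two-sided 5%, counting only significant improvement (nominal 2.5%).

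The paired test stands in for the within-group time effect. The plan does not specify it.

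**4. Fresh post-screening baseline, no CBT effect.** The SD of the change is 2 × √(2(1 − rho)), which is 1.79, 1.55 and 1.26 for rho 0.6, 0.7 and 0.8. The chance of significant improvement is the probability that a non-central t variable with n − 1 degrees of freedom and non-centrality delta × √n / SD(change) exceeds the 97.5% point of t. For n = 18, rho 0.6 and delta 0.5, the non-centrality is 0.5 × 4.243 / 1.789 = 1.19 and the probability is 0.20.

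| delta | n = 18, rho 0.6 / 0.7 / 0.8 | n = 36, rho 0.6 / 0.7 / 0.8 |
|---|---|---|
| 0 | 2.5% throughout | 2.5% throughout |
| 0.5 | 20% / 25% / 35% | 37% / 47% / 64% |
| 1.0 | 61% / 73% / 89% | 90% / 96% / 100% |

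Simulation with selection at above 4 agrees: 2% to 3%, 20% to 36% and 61% to 89% at n = 18. The assumed mean does not matter here, because selection acts on a different measurement from the baseline.

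**5. Screening BPI used as baseline.** Expected regression to the mean is SD × (1 − rho) × φ(z) / (1 − Φ(z)), with z = (4 − mean)/SD.
- Mean 4.5, rho 0.6: z = −0.25, and 2 × 0.4 × 0.387/0.599 = 0.52 points.
- Mean 6.0, rho 0.8: z = −1, and 2 × 0.2 × 0.242/0.841 = 0.12 points.

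Simulated at n = 18 with no other change, this gives significant improvement in about 5% to 23% of trials. Adding 0.5 point of non-specific change gives about 40% to 70%.

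**6. Concurrent control.** When both arms share the same non-specific change, a two-arm comparison of change rejected in about 4% to 6% of simulated trials in every scenario (nominal 5%, two-sided).

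**The case against.** **The design already has a CBT factor.** The overview lists an education-only control, the power text discusses main and interaction effects, and 18 per group out of 72 fits four cells. This stands in part. A reader might infer that 1a can only mean an uncontrolled pre-post test, or that the trial has no control for CBT. The documents support neither: 1a is ambiguous, and a factorial analysis may be intended. But the intention appears only in the overview and the power text, not in the hypothesis or the model.

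**The run-in deals with regression to the mean.** A reader might infer that selecting for BPI above 4 would by itself tend to confirm 1a. With a fresh baseline, such as the two-week diary, the rate is nominal. The plan does not say which baseline 1a uses, so this objection disposes of the selection argument only if the run-in supplies the baseline. The BPI entry rule also appears only in section E.1, not in the Participants paragraph.

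**Non-specific improvement in pain is assumed.** Correct. In the cited sham-controlled right-prefrontal rTMS trial, "Both groups improved in fatigue and CGI", but pain did not improve, so it cannot be used as evidence of non-specific pain relief. The 0.5 and 1.0 point values are illustrations.

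**The next trial does not rest on 1a.** Largely right. Section E.4 ties follow-on work mainly to tDCS combined with CBT, which is 1b, a randomised contrast that this point leaves untouched. This is also a pilot. Both facts lower the severity.

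**Conclusion.** The concern holds as a defect of specification. Hypothesis 1a has no comparator, the stated model has no CBT term, and the sections disagree on whether an education-only arm exists. Read in the most natural way, 1a could be confirmed with no CBT effect in about 20% to 35% of trials at n = 18 if non-specific improvement were 0.5 point, and in about 61% to 89% if it were 1.0 point, against 2.5% nominal. These figures rest on an assumed SD of 2, a correlation of 0.6 to 0.8, a fresh baseline and a paired test; none of these comes from the documents. With no non-specific change and a fresh baseline there is no inflation. Regression to the mean is a secondary, conditional threat. The point should be fixed, but it does not undermine the tDCS comparison in 1b.

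**What to change.** 1. Reconcile the Overview, Procedures and Data Analysis Plan in section D with section E.3 on whether education-only arms exist.
2. If they do, restate 1a as greater change in pain and functioning with CBT plus sham tDCS than with education-only plus sham tDCS. Add a CBT-versus-education-by-time term to the hierarchical linear model.
3. Name a post-screening, pre-treatment baseline: the two-week diary mean for pain, and a separately collected post-screening value for functioning, which the diary does not replace.
4. If every patient receives CBT, state that 1a is descriptive and supports no conclusion on CBT efficacy.

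**Cost.** One reworded hypothesis, one model term and a baseline definition, with no added patients provided the education arms are already planned. If they are not, only the descriptive option is free. A post-screening functioning measurement may add one questionnaire if none is scheduled. The between-arm test is less likely to reach significance than the pre-post change: with 18 against 18 and an assumed standardised difference of 0.5, two-sided power is about 0.31. That is a limit of the sample size, not a reason to keep an uncontrolled test. The contrast also removes attention effects only as far as the education sessions match CBT for contact, which the protocol should describe.
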